8.3.3.3 Acute-phase Reactant

ESR and CRP will be obtained in the RA-specific laboratory panel (see Table 7). This assessment will be used as an input parameter for 2010 ACR/EULAR score and DAS28 score.

8.4 Imaging

8.4.1 Image Acquisition

8.4.1.1 Planar Scintigraphy

Bilateral hand and wrist planar image acquisition occurs in Arm 1 and 2 subjects beginning 60-75 minutes following Tc 99m tilmanocept injection. Refer to the NAV3-35 Image Acquisition Guidelines for all required imaging technical specifications and acquisitions.

8.4.1.2 SPECT/CT

SPECT/CT is performed for Arm 2 subjects on the bilateral hands and wrists only following the planar scan. Refer to the NAV3-35 Image Acquisition Guidelines for all required imaging technical specifications and acquisitions. SUV will be calculated for DAS28 joints of interest according to standard methods. See the NAV3-35 Image Review Charter and Statistical Analysis Plan for more details.

8.4.2 Tilmanocept Uptake Value (TUV)

TUV is a quantitative imaging metric used to characterize the amount of CD206 activity on planar imaging. Results from prior Phase 1 and 2 studies have demonstrated that TUV is a sensitive and specific predictor of visually interrogated Tc 99m tilmanocept localization in joint regions with presumed inflammatory macrophage activity. A per-joint TUV (TUV_{joint}) relative ratio will be calculated for the each of the 22 DAS-28 joints located in the hands and wrists. A subject-level global TUV (TUV_{global}) assessed across the 22 joints will be used as an indication of overall disease burden.

For all subjects, delegated trained imaging scientists blinded to all clinical subject information will perform semi-automated ROI drawing on planar images of the bilateral hands and wrists to derive relevant count statistics, which are input parameters for TUV_{joint} and TUV_{global}. TUV metrics are further described in the NAV3-35 Statistical Analysis Plan.

8.5 Adverse Events

8.5.1 Definition of Adverse Event

The definitions below follow International Conference on Harmonization (ICH) – Good Clinical Practice (GCP) (see also ICH Guideline for Clinical Safety Data Management: Definitions and Standards for Expedited Reporting).

An AE is defined as any untoward medical occurrence in a subject administered a pharmaceutical product and which does not necessarily have a causal relationship with this treatment. An AE can therefore be any unfavorable and unintended sign (including an abnormal laboratory finding), symptom, or disease temporally associated with the use of a medicinal (investigational) product, whether or not considered related to the medicinal (investigational) product.

Any clinically significant change in a condition (worsening) from screening that results in a change in subject management will be considered an AE and will be recorded on the AE page of the CRF.

By definition for this study, all untoward medical occurrences beginning on the Visit 2 (Day 0) until the final visit (variable per arm) are to be reported as AEs. AEs continuing after study completion will be followed to normalization or stabilization. Additionally, untoward medical events occurring prior to the day of Tc 99m tilmanocept administration will be collected and added to the subject's medical history unless they are related to a study procedure, in which case the event will be recorded as an AE. SAEs will be reported from the time of consent through the end of participation.

8.5.2 Categories for Adverse Event Assessment

The severity of an AE is classified according to the following categories, taking into account the possible range of the intensity of the event:

- Mild The adverse event is transient and easily tolerated by the subject.
- Moderate The adverse event causes the subject discomfort and interrupts the subject's usual activities
- Severe The adverse event causes considerable interference with the subject's usual activities and may be incapacitating or life-threatening.

Specific drug treatment

Any specific drug treatment will be documented.

Causal relationship to investigational product

The investigator will use the following definitions to assess the relationship of the adverse event to the use of investigational product:

Definitely related:	Event can be fully explained by administration of the investigational product.
Probably related:	Event is most likely to be explained by administration of the investigational product rather than the subject's clinical state or other agents/therapies.
Possibly related:	Event may be explained by administration of the investigational product or by the subject's clinical state or other agents/therapies.
Probably not related:	Event is most likely to be explained by the subject's clinical state or other agents/therapies, rather than the investigational product.

Definitely not related: Event can be fully explained by the subject's clinical state or other agents/therapies.

For causality assessments, events meeting the categories of definitely, probably, or possibly related will be considered to be related to investigational product.

Causal relationship to study procedure

The investigator will use the following definitions to assess the relationship of the adverse event to study procedure:

Definitely related:	Event can be fully explained by the study procedure.
Probably related:	Event is most likely to be explained by the study rather than the subject's clinical state or other agents/therapies.
Possibly related:	Event may be explained by the study procedure or by the subject's clinical state or other agents/therapies.
Probably not related:	Event is most likely to be explained by the subject's clinical state or other agents/therapies, rather than the study procedure.
Definitely not related:	Event can be fully explained by the subject's clinical state or other agents/therapies.

For causality assessments, events meeting the categories of definitely, probably, or possibly related will be considered to be related to study.

8.5.3 Assessments and Documentation of Adverse Events

Attention shall be paid to the occurrence of AEs for the duration of subject participation. Events occurring prior to Visit 2 (Day 0) will be recorded in the subject's medical history unless related to study procedure, in which case the event will be recorded as an AE. Untoward medical events beginning on Visit 2 (Day 0) until the final visit (variable per arm) will be reported as adverse events.

Any AE (observed, volunteered, or elicited) should be recorded in detail in the source documentation.

The following information is required:

- The **date** and **time of onset** of any AE.
- The duration (the entire duration of an event or symptom, calculated from date of onset to date of end, if not recorded directly).
- The seriousness of the AE will be assessed by the investigator. If the investigator deems that an AE qualifies as an SAE, a special form provided by the sponsor should be completed and the event must be immediately reported to the sponsor. A definition of serious adverse events is provided in Section 8.5.5.

- The maximum intensity (mild, moderate, or severe).
- Whether drug treatment was administered for the event, any specific drug treatment must be documented.
- The relationship of the AE to the investigational product and to study conduct (for definitions, see above).
- The **outcome** of the AE (resolved, resolved with sequelae, not resolved, unknown, death).

AEs will be coded according to an internationally recognized dictionary (Medical Dictionary for Regulatory Activities [MedDRA]).

8.5.4 Expected Adverse Events

Investigational Product-Related Risks

In all completed studies of Lymphoseek (Tc 99m tilmanocept), involving 553 subjects, only 3 events (breast pain and injection site pain reported by subjects with breast cancer and injection site irritation reported by a subject with head and neck squamous cell cancer) were deemed definitely related to the administration of Lymphoseek by the investigator. The most common adverse reactions (incident < 1%) have been lack of effect (< 0.067%), injection site pain (< 0.02%) and rash (< 0.02%). Adverse events from the radioactive dose are not expected, since the applied radiation doses are far below doses that can cause acute effects in human tissues. Routes of administration included: subcutaneous, intradermal, and peritumoral.

In addition to the Lymphoseek pre-approval clinical studies, post-marketing surveillance shows that Lymphoseek has been administered to more than 450,000 patients with not a single drug-related SAE. Routes of administration included: subcutaneous, intradermal, and peritumoral.

The intended route of administration in this study is intravenous. There have been approximately 280 IV administrations of Tc 99m tilmanocept to date, and no SAEs or AEs related to the product have been reported to date.

Risks of Imaging Procedures

Radiation dose considerations from Tc 99m Tilmanocept planar and SPEC/CT scans – Patients enrolled in this trial will have hand/wrist planar gamma camera scans following Tc 99m Tilmanocept injection, with subjects enrolled in Arm 2 also receiving one hand/wrist SPECT/CT scan.

The average effective radiation dose per 10 mCi Tc 99m Tilmanocept injection is calculated to be 2.7 mSv (equivalent to about ten months of natural background radiation received in the US). Subjects enrolled in Arm 1 will receive one injection, equal to 2.7 mSv total; subjects enrolled in Arm 2 will receive one injection plus one SPECT/CT scan- with an estimated effective dose of 1 mSv for the CT portion- amounting to 3.7 mSv total. Therefore, the maximum possible dose of \sim 3.7 mSv for any enrolled subject (no one will cross over into more

than one study arm) is considered to be a minor to intermediate risk level corresponding to the benefit to the patient [category IIb based on the International Commission on Radiological Protection 62 (ICRP62)] and is balanced against the possible substantial societal benefit that can be gained from the trial (European Commission Radiation Protection 99, 1998 and ICRP 62, 1992). For further reference, the effective dose from a standard CT abdomen and pelvis, with and without contrast, is up to 20 mSv.

Precautionary Measures

Special precautionary measures are not considered necessary for this study. In case of emergency, standard emergency procedures will be employed.

Unexpected Adverse Events

An unexpected adverse event is defined as an adverse reaction that in nature and severity is not consistent with the applicable product information (e.g., Investigator's Brochure). Any adverse experience that is not listed in the current Investigator's Brochure or which is, with regard to the specificity or severity, not consistent with the risk information shall be regarded as unexpected.

Examples would be (a) acute renal failure listed in the Investigator's Brochure with a subsequent new report of interstitial nephritis and (b) hepatitis with a first report of fulminant hepatitis. "Unexpected" as used in this definition refers to an adverse drug experience that has not been previously observed and included in the Investigator's Brochure, rather than from the perspective of such experience not being anticipated from the pharmacological properties of the investigational product.

8.5.5 Serious Adverse Events

Definition of Serious Adverse Events

The following SAE definition is based on ICH guidelines and the final rule issued by the Food and Drug Administration (FDA) and effective 06 Apr 1998.

An SAE is classified as any untoward medical occurrence that at any dose:

- results in death, or
- is life threatening, or
- requires inpatient hospitalization or prolongation of existing hospitalization, or
- results in persistent or significant disability/incapacity, or
- is a congenital anomaly/birth defect, or
- is an important medical event (see paragraphs below).

The term 'life threatening' in the definition refers to an event in which the subject was at risk of death at the time of the event; it does not refer to an event that hypothetically might have caused death if it were more severe.

Medical and scientific judgment should be exercised in deciding whether it is appropriate to report an AE as serious also in other situations, such as important medical events that may not be immediately life threatening or result in death or hospitalization but may jeopardize the subject or may require intervention to prevent one of the other outcomes listed in the definition above. These should also usually be considered serious. Examples of such events are intensive treatment in an emergency room or at home for allergic bronchospasm or blood dyscrasias or convulsions that do not result in subject hospitalization.

Actions and reporting obligations in case of serious adverse events

The investigator should take appropriate diagnostic and therapeutic measures to minimize the risk to the subject.

If any SAE occurs over the course of the study, investigators or other site personnel will inform Navidea Biopharmaceutical representatives within 1 day (i.e., within 24 hours) of becoming aware of the SAE. Written notification of the SAE will be emailed to Navidea Biopharmaceuticals Pharmacovigilance at [contact]. For fatal or life-threatening adverse events where important or relevant information is missing, active follow-up is undertaken immediately.

Pregnancy will have the same time reporting obligations to the sponsor as SAEs. Upon notification, Navidea will provide a form for collection of pregnancy information.

All SAEs must also be recorded on the Adverse Event eCRFs.

Notification of the IRB(s)

The sponsor and/or the investigator will notify the IRB(s) about all relevant events (e.g., serious adverse events [SAEs] and Suspected, Unexpected, Serious Adverse Reactions [SUSARs]) according to all applicable regulations.

Notification of the authorities

The sponsor will process and report all relevant events (e.g., SAEs, SUSARs) to the authorities according to all applicable regulations.

Sponsor's notification of the investigators

The sponsor will inform all investigators about reported relevant events (e.g., SAEs, SUSARs) according to all applicable regulations.

8.6 Physical Examination

Complete physical examinations will be conducted at screening including height and weight assessments. A physical exam that has been conducted as standard of care prior to signing informed consent may be used if it was performed within 30 days of injection.

Physical examinations will be performed for the following body systems:

- General Appearance
- Skin/dermatological
- Eyes, ears, nose, throat
- Head and neck (including thyroid)
- Lungs
- Heart
- Abdomen (liver, kidney, spleen, gastrointestinal)
- Lymph nodes
- Musculoskeletal
- Nervous system

8.7 Vital Signs

Vital signs comprise the measurement of body temperature, heart rate, respiration, systolic and diastolic blood pressure. All measurements will be taken after the subject has been in a resting position for at least 1 minute. Vital signs will be measured at screening, within 30 minutes before investigational product injection, and within 30 minutes post injection. Any clinically significant change from screening (worsening) that results in a change in subject management will be considered an AE and will be recorded on the AE page of the CRF.

9 STATISTICAL METHODS

This is a prospective, open-label, multicenter study of the patterns of variation in planar imaging using IV injected Tc 99m tilmanocept for the quantitative detection of disease activity in the skeletal joints of HC subjects and subjects with active RA. In addition to quantitative assessments, this study will also include qualitative (i.e., visual) evaluations of SPECT/CT in detecting localization within synovial spaces of the bilateral hands and wrists.

The study is stratified into 2 groups. Arm 1 consists of HC subjects. Arm 2 consists of HC subjects and RA subjects on stable therapy.

9.1 Randomization Methods

This study is not randomized.

9.2 Safety Variables

The safety analysis variables are defined as follows:

- Adverse events (AEs)
- Clinical laboratory tests (hematology, serum chemistry, urinalysis, and RA panel)
- Vital signs

9.3 Efficacy Variables

The efficacy variables for this study are defined below:

- Quantitative determination of TUV_{joint} and TUV_{global}
- Qualitative (i.e., visual) determination of tilmanocept localization in planar and SPECT/CT images of the bilateral hands and wrists;
- Quantitative determination of tilmanocept localization in planar and SPECT/CT images of the bilateral hands and wrists.

It is presumed that the presence of radiotracer uptake for a joint indicates the presence of activated macrophages. The use of the term "localization" is synonymous with radiotracer uptake.

The efficacy endpoints for this study, by arm, are as follows:

Primary Endpoint(s)

ARM 1

• The normal limits of TUV_{joint} (on a per joint basis) in HC subjects, which are defined as the 5 and 95 percentiles of TUV_{joint} of bilateral joints (i.e., bilateral wrists, metacarpophalangeal joint [MCPs], proximal interphalangeal [PIPs]). The normal range will be determined separately for each of the three blinded readers.

ARM 2

• The qualitative evaluations of SPECT/CT in detecting localization within synovial spaces of the bilateral hands and wrists in HCs and RA subjects.

Secondary Endpoints

ARM 1

• Applicability of the Normal (Gaussian) distribution to TUV_{joint} data.

ARM 2

- Quantitative evaluations of Tc 99m tilmanocept localization from SPECT/CT within synovial spaces of the bilateral hands and wrists in HCs and RA subjects.
- Normative joint-specific SUV.
- Predictive value of planar scans for SPECT/CT scans.

9.4 Sample Size Justification

The study will enroll up to 135 evaluable subjects in Arms 1 and 2 allocated below, imaged at up to 8 study centers. Arm 1 will have N = 120 evaluable HC subjects, Arm 2 will have N = 15 (5 HCs and 10 RA) evaluable subjects. A subject is considered evaluable if he/she meets the criteria for the analysis population and has the data necessary for computing the primary endpoint.

The sample size for Arm 1 was determined to provide acceptable precision for the estimated 5 and 95 percentiles. These percentiles will be estimated with 95% nonparametric confidence intervals. Although the standard error formula for quantile estimators is known and quantile estimators obey a central limit theorem, relying on the asymptotic Normal distribution seems imprudent.

The sample will be stratified 3:1, females:males to reflect RA incidence in the United States [58, 59]. The sex-specific samples will be further stratified by age to reflect the Census estimated US population in 2019 (U.S. Census Bureau, 2020 [60]). The target sample sizes are given below.

Age Range	Male	Female	Total
30 to 39 years	8	23	31
40 to 49 years	7	21	28
50 to 59 years	8	22	30
60 to 69 years	7	21	28
70 years and older ^a	6	21	27
Total	36	108	144

^a An effort will be made to target enrollment in this group to include 2 men and 8 women 80 years old and over.

The existing data for HC subjects was used in a bootstrap procedure to evaluate the width of 95% confidence intervals for the 95 percentiles for various sample sizes. The sponsor has decided for its business purposes that knowing the percentile to within 0.05 of its true value is sufficient. A sample of size N = 144 HC results (this includes the subjects from Arm 1 of NAV3-31) in 95% confidence intervals with half-widths less than 0.05.

The sample size for Arm 2 was determined to be sufficient for the business purposes of the sponsor. The sample size for Arm 2 will be 5 HCs and 10 RA subjects.

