The sample size for Arm 1 was determined to provide acceptable precision for the estimated 5 and 95 percentiles. These percentiles will be estimated with 95% nonparametric confidence intervals. Although the standard error formula for quantile estimators is known and quantile estimators obey a central limit theorem, relying on the asymptotic Normal distribution seems imprudent.

The sample will be stratified 3:1, females males to reflect RA incidence in the United States. The sex-specific samples will be further stratified by age to reflect the Census estimated US population in 2019. The target sample sizes are given below.

Age Range	Male	Female	Total	
30 to 39 years	8	23	31	-
40 to 49 years	7	21	28	
50 to 59 years	8	22	30	
60 to 69 years	7	21	28	
70 years and older ^a	6	21	27	
Total	36	108	144	

^a An effort will be made to target enrollment in this group to include 2 men and 8 women 80 years old and over.

The existing data for HC subjects was used in a bootstrap procedure to evaluate the width of 95% confidence intervals for the 95 percentiles for various sample sizes. The sponsor has decided for its business purposes that knowing the percentile to within 0.05 of its true value is sufficient. A sample of size N = 144 HC results (this includes the subjects from Arm 1 of NAV3-31) in 95% confidence intervals with half-widths less than 0.05.

The sample size for Arm 2 was determined to be sufficient for the business purposes of the sponsor. The sample size for Arm 2 will be 5 HCs and 10 RA subjects.

Assessments:

Efficacy Primary Endpoint(s)

ARM 1

The normal limits of TUV_{joint} (on a per joint basis) in HC subjects, which are defined as the 5 and 95 percentiles of TUV_{joint} of bilateral joints (i.e., bilateral wrists, metacarpophalangeal joint [MCPs], proximal interphalangeal [PIPs]). The normal range will be determined separately for each of the three blinded readers.

ARM 2

• The qualitative evaluations of SPECT/CT in detecting localization within synovial spaces of the bilateral hands and wrists in HCs and RA subjects.

Secondary Endpoints

ARM 1

• Applicability of the Normal (Gaussian) distribution to TUV_{joint} data.

ARM 2

- Quantitative evaluations of Tc 99m tilmanocept localization from SPECT/CT within synovial spaces of the bilateral hands and wrists in HCs and RA subjects.
- Normative joint-specific standardized uptake value (SUV).
- Predictive value of planar scans for SPECT/CT scans.

Statistical Methods:

Primary Endpoint Arm 1

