9.5 Statistical Analyses

9.5.1 Analysis Populations

The following populations are defined for this study:

Intent-to-Diagnose (ITD) Population – the ITD population includes all subjects who have been enrolled in the study, injected with Tc 99m tilmanocept, and received all imaging and evaluations necessary for the primary endpoint(s) appropriate to their respective arm.

Per-Protocol (PP) Population – the PP population consists of all ITD subjects without major protocol violations.

Safety Population – The safety population includes all subjects who have been enrolled in the study and injected with Tc 99m tilmanocept.

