#### 1.3 Sample Size

The study will enroll up to 135 evaluable subjects in Arms 1 and 2 allocated below, imaged at up to 8 study centers.

Arm 1 will have up to N = 120 evaluable HC subjects, Arm 2 will have up to N = 15 evaluable subjects; 5 HCs and 10 RA subjects.

A subject is considered evaluable if he/she meets the criteria for the analysis population and has the data necessary for computing the primary endpoint(s) relevant to his/her study Arm.

The sample will be stratified 3:1, females to males ratio to reflect RA incidence in the United States. The sex-specific samples will be further stratified by age to reflect the Census estimated US population in 2019.

The target sample sizes are given below.

Age Range	Male	Female	Total
30 to 39 years	8	23	31
40 to 49 years	7	21	28
50 to 59 years	8	22	30
60 to 69 years	7	21	28
70 years and older	6	21	27
Total	36	108	144

An effort will be made to target enrollment in this group to include 2 men and 8 women 80 years old and over.

The existing data for HC subjects was used in a bootstrap procedure to evaluate the width of 95% confidence intervals for the 95 percentiles for various sample sizes. The sponsor has decided for its business purposes that knowing the percentile to within 0.05 of its true value is sufficient. A sample of size N = 144 HC results (this includes the subjects from Arm 1 of NAV3-31) in 95% confidence intervals with half-widths less than 0.05.

The sample size for Arm 2 was determined to be sufficient for the business purposes of the sponsor. The sample size for Arm 2 will be 5 HCs and 10 RA subjects.

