#### 2.2 Analysis Populations

The following analysis populations will be used in the study:

**Safety Population** – The safety population includes all patients that have been enrolled in the study and injected with Tc 99m tilmanocept.

**Intent-to-Diagnose (ITD) Population** – The ITD population includes all subjects that have been enrolled in the study, injected with Tc 99m tilmanocept, and

received all imaging and evaluations necessary for the primary endpoint(s) appropriate to their respective arm.

**Per Protocol (PP) Population:** The PP population will include all ITD subjects without major protocol violations. All protocol violations will be classified as major or minor prior to database lock.

All efficacy analyses will be carried out on the ITD and PP populations with the ITD population being the primary analysis set. All analyses of safety data and baseline subject characteristics will be carried out on the safety population. A data listing displaying the patients excluded from each population will be created, as shown in Appendix B.

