# 7.0 List of Analysis Tables, Figures and Listings

Table No.	Table Title	Included in Final Tables	Shown in Appendix B
1	Subject Disposition by Study Arm	X	X
2	Demographics and Baseline Data Summary Statistics by Arm – Continuous Variables (Safety Population)	Х	Х
3	Demographics and Baseline Data Summary Statistics by Arm – Categorical Variables (Safety Population)	Х	Х
4	Summary of Study Drug Administration by Arm (Safety Population)	Х	Х
5	Summary of TUV joint on both Arms Per Reader, Joint, and View (ITD population)	Х	Х
6	Summary of TUV joint on both Arms Per Reader, Joint, and View (PP Population)	Х	
7	Summary of SUV on Arm 2 per Joint and a Total of All Joints (ITD population)	Х	Х
8	Summary of SUV on Arm 2 per Joint and a Total of All Joints (PP Population)	Х	
9	Normal Range of TUV joint for the Three Blinded Readers in All Arm 1 and 2 Healthy Control Subjects (ITD Population)	Х	Х
10	Normal Range of TUV joint for the Three Blinded Readers in All Arm 1 and 2 Healthy Control Subjects (PP Population)	Х	
11	Correlation Between TUV joint and Age and BMI – All Arm 1 and 2 Healthy Control Subjects (ITD Population)	Х	Х
12	Correlation Between TUV joint and Age and BMI – All Arm 1 and 2 Healthy Control Subjects (PP Population)	Х	
13	Frequency Counts and Percentage of Localization in SPECT/ CT Imaging in RA Subjects (ITD Population)	Х	Х
14	Frequency Counts and Percentage of Localization in SPECT/ CT Imaging in RA Subjects (PP Population)	Х	
15	Shapiro-Wilk P-Value for Normality Test for TUV joint Data – All Arm 1 and 2 Healthy Control Subjects (ITD Population)	Х	Х
16	Shapiro-Wilk P-Value for Normality Test for TUV joint Data – All Arm 1 and 2 Healthy Control Subjects (PP Population)	Х	
17	Predictive Value of Planar Scans for SPECT/CT Per Joint and Reader (ITD Population)	Х	Х
18	Predictive Value of Planar Scans for SPECT/CT Per Joint and Reader (PP Population)	Х	
19	Number and Percentage of Subjects with TEAEs (Safety Population)	Х	Х
20	Summary of TEAEs (Safety Population)	Х	Х
21	Number and Percentage of Subjects with TESAEs (Safety Population)	Х	Х
22	Number and Percentage of Subjects With TEAEs by Severity Grade (Safety Population)	Х	Х
23	Number and Percentage of Subjects With TEAEs by Level of Relationship to Tc 99m Tilmanocept (Safety Population)	Х	Х
24	Number and Percentage of Subjects With TEAEs by Level of Relationship to Procedure (Safety Population)	Х	

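### The half-width below 0.05 is stated only for 144 healthy controls including NAV3-31 Arm 1, but the written normal-range analysis holds at most 125

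*Protocol*

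**What the plan says.** **Sizing.** Protocol 9.4 says existing healthy-control data were bootstrapped "to evaluate the width of 95% confidence intervals for the 95 percentiles for various sample sizes". A result is given for one size only: "A sample of size N = 144 HC results (this includes the subjects from Arm 1 of NAV3-31) in 95% confidence intervals" whose half-widths are below 0.05. No figure is given for the 5th percentile, the other primary limit. The Synopsis and SAP 1.3 carry the same statement and the same age/sex target table, which totals 144. On the interval type, Protocol 9.4 says: "These percentiles will be estimated with 95% nonparametric confidence intervals".

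**Enrolment.** SAP 1.3: "Arm 1 will have up to N = 120 evaluable HC subjects, Arm 2 will have up to N = 15 evaluable subjects", of whom 5 are healthy controls and 10 have RA.

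**Analysis set.** Protocol 9.5.1: "the ITD population includes all subjects who have been enrolled in the study, injected with Tc 99m tilmanocept, and received all imaging" and evaluations needed for the primary endpoint. SAP 2.2 has the same definition, and PP is a subset of ITD. The title of SAP Table 9 gives the normal range "for the Three Blinded Readers in All Arm 1 and 2 Healthy Control Subjects (ITD Population"); Table 10 repeats it for PP. Protocol 9.5.3.4 takes the cut-off for a positive planar scan from Arm 1 results only. SAP 4.2.2 names no arm for that cut-off.

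**Pooling.** Protocol 3.1.2.3 says Arm 2 planar images will be pooled with data from this and earlier trials of the sponsor, for TUV evaluations that it does not specify. Protocol 8.1.1 ties the age and sex distribution of healthy controls in both arms to a normative database and refers to Section 9.4. SAP 2.5 refers to a normative data set. None of these lists the members.

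**The concern.** The precision figure is the only quantitative basis offered for the size of Arm 1, and it belongs to a larger data set than the one the plan analyses. A programmer who follows SAP 2.2, 4.2.1 and the table list will produce limits from this study's healthy controls alone.

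Those limits are the Arm 1 primary endpoint, and the 95th percentile also classifies planar scans as positive or negative in Arm 2. As written, a reader of the report cannot tell what precision the limits were designed to have, or whether NAV3-31 subjects ought to have been included.

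**Working it through.** **1. The plan's own figure.** It cannot be reproduced: the bootstrap data, the SD of TUVjoint, the half-width achieved at 144 and the unit resampled are not given. The target table does add up: 36 men + 108 women = 144, and by age 31 + 28 + 30 + 28 + 27 = 144.

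**2. Subjects available to the written analysis.**
- Tables 9 and 10: 120 (Arm 1) + 5 (Arm 2 healthy controls) = 125. Shortfall 144 − 125 = 19, or 13% of 144.
- Protocol planar cut-off: 120. Shortfall 144 − 120 = 24, or 17% of 144.

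Protocol 1.2.4.3 gives 105 evaluable subjects for NAV3-31 as a whole. The number in its Arm 1 is not stated, so whether it supplies 19 or 24 cannot be checked.

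**3. Effect on the half-width.** Assume the same unit in bootstrap and analysis, and a half-width proportional to 1/√n. The ratio to the value at 144 is √(144/n). The largest half-width at 144 that still keeps 0.05 at n is 0.05/√(144/n).

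| n | √(144/n) | Half-width if exactly 0.05 at 144 | Largest half-width at 144 that keeps 0.05 |
|---|---|---|---|
| 125 | 1.0733 | 0.0537 | 0.0466 |
| 120 | 1.0954 | 0.0548 | 0.0456 |

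As a check on the scaling, 40,000 simulated samples under an assumed Normal and an assumed lognormal shape (sigma 0.25) gave ratios of 1.06 to 1.07 at 125 and 1.09 at 120 for the sampling half-width of the 95th percentile.

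**4. What SD would make the difference matter.** This step assumes a Normal shape and uses the large-sample formula 1.96 × √(0.95 × 0.05/n)/φ(1.645), in SD units, where φ is the standard Normal density. It gives 0.345 at 144, 0.370 at 125 and 0.378 at 120. The largest SD that meets 0.05 is therefore 0.145, 0.135 and 0.132 in turn. Under this assumption the target is met at 144 but missed at 125 only for an SD between 0.135 and 0.145, and missed at 120 only for an SD between 0.132 and 0.145. The documents do not say where the SD lies.

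**5. The unit.** The Table 9 shell counts joints, so left and right may be combined, giving up to 2 × 125 = 250 values from 125 subjects. If the bootstrap used one value per subject, the effective number is 250/(1 + r), where r is the left-right correlation of the indicator of lying above the percentile. It reaches 144 when r = 250/144 − 1 = 0.74. Below that correlation the shortfall at 125 would vanish; above it, part remains. If the bootstrap also combined sides, the table in step 3 applies unchanged.

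**The case against.** The strongest reply is that pooling was intended and disclosed. The parenthesis about NAV3-31 Arm 1 stands in three places, the target table totals 144, Protocol 8.1.1 links the normative database to Section 9.4, and Protocol 3.1.2.3 speaks of pooling with earlier trials. On that reading the sizing is sound and only the documentation is short. As a reading of intent this is fair. It does not close the gap, because intent is not analysis: ITD requires enrolment in this study, and SAP 4.2.1 and Tables 9 and 10 contain no step that adds other subjects. The SAP describes summaries for this study's report. A pooled analysis may be planned elsewhere, but the documents do not say so.

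It can also be said that the loss is modest, that 0.05 is a threshold the sponsor set for its own purposes, and that no test or success rule depends on it. All of that stands and limits the weight of the point.

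Two stronger readings are tempting, and neither is supported. A reader might infer that the 0.05 target is missed. The documents report only that the value at 144 is below 0.05, so this cannot be concluded. A reader might also compute exact order-statistic intervals and infer a much larger loss. Those intervals move in rank jumps. Under an assumed Normal shape with at most 0.025 in each tail, the expected half-width is 0.456 SD at 125, but 0.477 SD at 128 and 0.469 SD at 140, before it falls to 0.393 SD at 143. A measure by which 140 subjects look less precise than 125 does not show the cost of losing 19 or 24.

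**Conclusion.** The concern holds as a mismatch between the sizing and the analysis set; it should be fixed but is not fatal. It rests on the text alone and is certain to that extent: precision is stated for 144 including external subjects, while the written analysis has at most 125, or 120 for the planar cut-off.

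The size is less certain. It is about 7% at 125 and about 10% at 120, on root-n scaling with a common unit, and could be smaller or nil if Table 9 combines left and right joints and the bootstrap did not. No conclusion about meeting or missing 0.05 is possible from the documents.

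**What to change.** Before database lock, do one of the following.

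**(a) Size for the subjects this study enrolls.** Report, or rerun, the existing bootstrap at the N and unit to be used for Tables 9 and 10 (125) and for the planar cut-off (120). Restate the half-width in Protocol 9.4, the Synopsis and SAP 1.3. Reset the age/sex target table in the same three places, since 125 healthy controls cannot fill 144 cells. Cost: at most one bootstrap run, as several sample sizes were already evaluated and the figure may exist, plus text edits. The restated half-width may exceed 0.05, and the sponsor would have to accept that openly.

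**(b) If 144 is intended, write the pooling into the SAP.** Define in SAP 2.2 a normative population that adds NAV3-31 Arm 1 healthy controls with comparable reader-specific reads, and state how many there are. Use it for Tables 9 and 10 and for the planar cut-off, in both Protocol 9.5.3.4 and SAP 4.2.2. Show the limits with and without NAV3-31. Cost: one new population, revised tables, one added display, access to the NAV3-31 data, and evidence that its reads are comparable, which the documents do not describe.

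Neither option needs more patients. Under Protocol 3.2, protocol changes that are more than administrative need a formal amendment.
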